#### 11.4 Source Records Used

- a. Permission/Accent or Consent Forms (Research Visit 1 or Phone Consent)
- b. Demographics (Research Visit 1 CRF)
- c. Prior/Concomitant Medications (Research Visit 1, Research Visit 2, Research Visit 3 and Research Visit 4 CRFs)
- d. Prior Medical History (Research Visit 1 CRF, Child Medical History Questionnaire)
- e. Needlestic and Pill Swallowing Questions (Research Visit 1 CRF)
- f. Vital Signs (Research Visit 1, Research Visit 2, Research Visit 3 and Research Visit 4 CRFs)
- g. Data from physical exam (Research Visit 1, Research Visit 2, Research Visit 3 and Research Visit 4 CRFs)
- h. Pregnancy status (Research Visit 1, Research Visit 2, Research Visit 3 and Research Visit 4 CRFs)
- i. Baseline and end of study electrocardiogram (Research Visit 1 and Research Visit 4 CRFs)
- j. Tanner Staging (Optional) (Research Visit 1, Research Visit 2, Research Visit 3 and Research Visit 4 CRFs)
- k. Genotyping data (Research Visit 2 and Research Visit 3 CRFs)
- l. Atomoxetine dose (IDS pharmacy prescriptions)

- m.* Pharmacokinetic Samples – plasma, urine, and sweat (Research Visit 1, Research Visit 2, Research Visit 3 and Research Visit 4 CRFs)
- n.* Pharmacodynamic Samples – plasma and serum (Research Visit 1, Research Visit 2, Research Visit 3 and Research Visit 4 CRFs)
- o.* Microbiome Samples – saliva (Research Visit 1, Research Visit 2, Research Visit 3 and Research Visit 4 CRFs)
- p.* CYP2D6 biomarker analysis – urine (Research Visit 1, Research Visit 2, Research Visit 3 and Research Visit 4 CRFs)
- q.* Attention Tasks – Pupillometry during Posner's Cuing Task data (data stored on computer hard drive, documentation in Research Visit 1, Research Visit 2, Research Visit 3 and Research Visit 4 CRFs)
- r.* Long-term dietary patterns – Dietary Survey Questionnaire (paper questionnaire)
- s.* Intelligence Quotient – Kaufman Brief IQ Test (KBIT) (paper questionnaire)
- t.* ADHD and comorbidities –
  - i.* Kiddie Schedule for Affective Disorders and Schizophrenia Present and Lifetime (K-SADS-PL) (paper questionnaire or KSADS-COMP);
    - 1. Subject Information (pages 1-3)
    - 2. Attention Deficit/Hyperactivity Disorder (pages 4-12)
    - 3. Generalized Anxiety Disorder (pages 13-17)
    - 4. Social Anxiety/Selective Mutism Disorder (pages 18-21)
    - 5. If KSADS-COMP is used, the above data are available electronically. These data will be downloaded and added to the participant binder.
  - ii.* Behavior Rating Inventory of Executive Function (BRIEF) (paper questionnaire);
  - iii.* Bradley Sluggish Cognitive Tempo Scale (paper questionnaire);
  - iv.* Screen for Child Anxiety and Related Disorders (CHADIS questionnaire);
  - v.* NICHQ Vanderbilt Assessment Scales for parent and teacher (CHADIS questionnaire);
  - vi.* Child Behavior Checklist (CHADIS questionnaire);
  - vii.* School Intervention Questionnaire (CHADIS questionnaire);
  - viii.* Clinical Global Improvement (Study Physician Note)

- u. Medication side effects –
  - i. Medication Side Effects (CHADIS questionnaire);
  - ii. In-person assessment (study CRFs and participant EMR);
  - iii. Parental reports (study CRFs and participant EMR if parent calls in and reports to a RN or physician on-call)
- v. Adverse events –
  - i. in person assessment (study CRFs and participant EMR);
  - ii. parental reports (study CRFs and participant EMR if parent calls in and reports to a RN or physician on-call)
- w. Study medication adherence – in person assessment (Research Visit 3, 6-Week Visit with Study Physician, 12-Week Visit with Study Physician, 18-Week Visit with Study Physician, and Research Visit 4 CRFs, Drug Adherence Calculator Excel Workbook)

#### **11.5 Continuing Care**

Additional clinical ADHD care will be at the discretion of the study physician, participant, and participant's family. This may include, but is not limited to, the following: 1) immediate transition of atomoxetine prescribing to the primary care physician or other specialist identified by the family, 2) continuation of atomoxetine prescribing and follow-up care by the study physician, 3) discontinuation or weaning of atomoxetine when deemed clinically appropriate. If the participant's ADHD care will be transitioned to their primary care provider or another community provider. A letter describing the course of the participant's care in the research trial will be provided to the family and the care provider. (See "End of Study ADHD Care Transition Letter" in the Appendix N)

#### **11.6 IBC**

The following IBC protocols will be used in this study:

- IBC Protocol #18-27 "Processing of Blood, Urine, Saliva, and Cerebral Spinal Fluid Samples from Clinical/Research Studies in the Clinical Pharmacology Research Laboratories"
- IBC Protocol #18-10 "Processing of Blood, Saliva, and Urine Samples from Clinical/Research Studies in the Pediatric Clinical Research Unit"

### **12.0 Data and Sample Banking**

- Data Banking Procedures: All data collected on study related CRFs and participant data on the EMR assessing participant outcomes (in

particular, participant safety, efficacy, and toxicity) will serve as source documents for this study. For ease of analysis and logistics of sharing data with the study team members, a subset of the complete dataset that are pertinent to assessing the research aims will be entered in a REDCap database. This is currently being developed and is tentatively titled, "U54 Longitudinal Atomoxetine – Clinical Outcomes 2.0." All study personnel, research associates, and U54 collaborators may have access to the data, however on a need to know basis.

- Sample Storing Procedures: Samples will be stored in –80 degree C freezers housed within the department of Clinical Pharmacology, Toxicology, and Therapeutic Innovation. These samples will be kept and stored here until all data analysis is complete and all findings from this research study have either been finalized or published. All study personnel, research associates, and U54 collaborators may have access to the samples. Following completion of this study and processing of all samples, these samples will be moved to the Pharmacokinetics/Pharmacodynamics (PK/PD) Repository (see the corresponding bullet point below)
- Procedures to release data or samples: Researchers within Children's Mercy Hospital, or their collaborators, who may find these data and/or specimens useful to answering future research questions may submit a written request to the PI of this study (in the event that data analysis and collection are still occurring) or the PI of the PK/PD Repository (following study completion). Permission will be granted by written letter by the respective principal investigator(s) (AppendixK). The distribution of data and/or samples will be facilitated by the PI and study personnel in the event that data and samples are shared prior to the conclusion of this study. Following the conclusion of this study and transfer to the PK/PD repository, release of data and specimens are the responsibility of the PK/PD Repository PI and Manager and will follow the protocol Pharmacokinetics/Pharmacodynamics Repository (IRB# TBD).
- Transfer to the Pharmacokinetics/Pharmacodynamics (PK/PD) Repository: Following conclusion of this study, samples will be transferred to the Pharmacokinetics/Pharmacodynamics Repository which will be maintained by the Children's Research Institute Biorepository (CRIB). The Pharmacokinetics/Pharmacodynamics Repository will be an identified repository which is comprised of clinical data, research data, and biological samples (e.g. blood, urine, tissue

samples, etc.) that may be used prospectively to answer research questions relating to pediatric clinical pharmacology. The data distributed for prospective future research will be de-identified by CRIB personnel as is described in the PK/PD Repository protocol (IRB # TBD).

- Samples from minors, plan for re-contacting and obtaining consent: The study population will include minors whose samples will be retained for long term research. The permission/assent and consent forms for this study will provide participants with the option of allowing retention of their samples and data in the PK/PD Repository for prospective future studies. If the participant turns 18 at the time of data collection, the participant will be reconsented. If the participant turns 18 after data collection has taken place, no attempt shall be made to recontact the participant (see section 25.0).

### **13.0 Genetic Analysis Information**

- Genome-wide analysis and single nucleotide polymorphism (SNP) analysis will be conducted on participant samples.
- We do not expect to discover paternity findings, as we are not enrolling trios in this study. However, given that we are assaying for genetic variants in biochemical pathways that affect neurotransmitter levels and activity, it is possible that findings may be made regarding other diseases. In particular, findings may be made where there is significant overlap between ADHD and the disease in question, such as autism or anxiety.
- Genetic testing (microarray SNP analysis, PCR sequencing, etc.) to determine ATX dose and study design will not be conducted in a CLIA-certified lab. Genome-wide testing will be conducted at the Children's Mercy Hospital Genome Center, which is CLIA-certified. Additional testing may be conducted should more information regarding genes associated with ATX pharmacokinetic, pharmacodynamic, and clinical outcomes become available. The assays may be conducted in either the Clinical Pharmacology laboratories or at the Genome Center, depending on assay availability.

## 14.0 Sharing of Results with Subjects

- Sharing Results with Participants: Results from genetic testing of pharmacogenes, such as, *CYP2D6*, *CYP2C19*, *CYP2B6*, etc. will be shared with participants and their families. In particular, *CYP2D6* genetic information will be pertinent to research participants as this result determines the duration of Research Visit 2, Research Visit 3, and Research Visit 4. *CYP2C19* data will also be shared given the number of available medication guidelines written for this pharmacogene. Should additional actionable pharmacogene information become available during the course of this study, further information may be shared with the family. Genetic information will be explained in a letter (Appendix L) to the participant/family. The letter will state that the genotyping information obtained from this study are research results that are used to achieve the research goals of this study. These results were obtained from our research lab which does not adhere to CAP/CLIA guidelines. Because of this, these results cannot be included in the participant's medical record and should not be used to make medical decisions. The research team will inform participants/families that the Genotype- and Ontogeny Linked Dose Individualization and Clinical Optimization for Kids (GOLDILOKs) Clinic can facilitate obtaining genetic testing that is CAP/CLIA certified at the expense of the participant. Additionally, the GOLDILOKs Clinic can interpret the genetic results obtained from CAP/CLIA labs for the participant and their families. The results obtained by the GOLDILOKs clinic can be documented in the participant's medical record for future medical decision-making. This practice complies with the CRI Policy and Procedure, "Research Documentation in the Electronic Health Record" approved on 09/26/2019.
- Sharing Incidental Findings with Participants: Incidental findings that are discovered during the course of this study may be released to participants and their families for the purposes of seeking further care (Appendix M).
- Sharing Results with Providers: Participant results from genetic testing of pharmacogenes will be documented in the EMR if the family requests a referral to the GOLDILOKs Clinic for further interpretation of genetic results. However, this note will include a statement that these data were not obtained from a CLIA-certified lab. At the end of the study, or when the study participant withdraws or is lost to follow-up, a final research note will be included to describe the atomoxetine regimen for the participant while in the study. This note will be forwarded to

the Study Physician to aid in the transition of care of the participant from the study to a healthcare provider.

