## 18.0 Potential Benefits to Subjects

- Personalized Medication Dosing: Participants will receive more personalized dosing of atomoxetine therapy through participation in study.

- **Genetic Information:** Participants will have genetic information returned to them (as it is related to duration of study visits) and will be given information about the GOLDILOKs Clinic at Children Mercy's Hospital where they can learn about the impact that their unique genetic information has on the way their body processes ATX and numerous other medications. As mentioned previously in section 14.0, it will be explained to families that genetic testing results obtained as part of the study cannot be used by GOLDILOKs Clinic for interpretation, but rather, that the testing will need to be repeated in a CLIA-certified lab. If the participant and/or family would like to be seen in GOLDILOKs Clinic and repeat genetic testing, these services will not be paid for by the study and will be the responsibility of the participant/family.

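### Section 14.0 both bars uncertified research genotypes from the medical record and requires their entry when a family asks for a GOLDILOKs referral, for a purpose section 18.0 says the clinic cannot serve

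*Combined protocol and SAP*

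**What the plan says.** Section 13.0 states that the genotyping used "to determine ATX dose and study design will not be conducted in a CLIA-certified lab". Three later statements set out what may be done with the results.

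- **Section 14.0, *Sharing Results with Participants*.** Pharmacogene results go to families by letter (Appendix L). They come from a research laboratory that does not work to CAP/CLIA guidelines, and for that reason "these results cannot be included in the participant's medical record and should not be used to make medical decisions". The GOLDILOKs Clinic can arrange certified testing at the family's expense, and "The results obtained by the GOLDILOKs clinic can be documented in the participant's medical record for future medical decision-making". The practice is said to comply with a named institutional policy on research documentation in the health record, dated 09/26/2019.
- **Section 14.0, *Sharing Results with Providers*.** Here the rule reads: "Participant results from genetic testing of pharmacogenes will be documented in the EMR if the family requests a referral to the GOLDILOKs Clinic", the referral being "for further interpretation of genetic results". The text adds that "this note will include a statement that these data were not obtained from a CLIA-certified lab".
- **Section 18.0, genetic information.** Families are to be told that study results "cannot be used by GOLDILOKs Clinic for interpretation, but rather, that the testing will need to be repeated in a CLIA-certified lab".

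**The concern.** Two bullets of one section give staff opposite instructions about the same data. The participant bullet bars the research genotype from the record and names no exception for referrals. The provider bullet requires entry once a referral is requested. Section 18.0 then says the clinic cannot do with the study result what the provider bullet appears to send the family there for.

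Two things are at stake. The first is the accuracy of what families are told: they hear that the result cannot enter the record, and taking up the study's own suggestion puts it there. The second is that a CYP2D6 or CYP2C19 result in a medical record bears on drugs other than atomoxetine and remains after the study ends. The participant bullet itself notes how many medication guidelines exist for CYP2C19. An uncertified result could therefore be consulted later, although the protocol says it should not guide medical decisions.

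**Working it through.** No arithmetic applies, because the plan gives no figure on this point. The check is a comparison of texts.

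**Step 1. Are the two bullets in section 14.0 about the same data?** The provider bullet could in principle mean the clinic's own certified repeat result. Its next sentence rules that out, since it requires the note to say that "this note will include a statement that these data were not obtained from a CLIA-certified lab". A certified repeat would need no such label. Section 13.0 mentions that genome-wide testing is done in a CLIA-certified centre, but both bullets in section 14.0 treat the shared pharmacogene results as uncertified. The subject is therefore the study's own research genotype in both places.

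**Step 2. Compare the rules.**

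| Question | 14.0, participants | 14.0, providers | 18.0 |
|---|---|---|---|
| May the research genotype enter the record? | No | Yes, on referral, with a label | Not addressed |
| May it be used? | Not for medical decisions | Referral is for interpretation of genetic results | Not by the clinic for interpretation |
| What is the certified route? | Clinic arranges certified testing, and those results can be recorded | Not mentioned | Repeat in a CLIA-certified laboratory |

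**Step 3. Which conflicts are direct?** The first row is: one bullet forbids what the other requires, and no action satisfies both once a referral is requested. The second row is weaker. The provider bullet and section 18.0 could both be followed by entering a labelled note, making the referral and repeating the test. They clash over the stated purpose of the referral, not over whether a referral may happen.

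**Step 4. Who is affected?** Only children whose families request the referral. The ceiling is the enrolment target of 160 (sections 1.0 and 8.0). The protocol gives neither the expected uptake nor an error rate for the research genotyping, so no count of affected or miscalled children follows from it.

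**The case against.** The strongest defence is that the provider bullet is a badly worded exception. The bar on the record comes just after a description of what the family letter will say, while the other bullet concerns communication with clinicians. On this view a labelled note, for families who choose referral to the clinic that arranges certified testing, is a reasonable hand-over. Part of this stands: the label reduces the risk of misuse, and the referral leads towards a certified repeat, though the family must pay for it. But the bar is stated without exception, and if it is wording for the letter, the letter would tell families something the next bullet contradicts. A label does not reconcile a prohibition with a requirement.

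Four stronger readings are tempting, and the documents do not support them.

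- **That the provider bullet breaches institutional policy.** Only the title and date of the policy appear. It might permit labelled research entries. What can be shown is that the bullet contradicts the rule stated beside it.
- **That only the certified repeat may ever be recorded.** The participant bullet says clinic-obtained results can be recorded. The exclusion of study results comes from its separate sentence, "these results cannot be included in the participant's medical record and should not be used to make medical decisions".
- **That the research genotypes are known to be unreliable.** Section 5.1 allows more genotyping when genotype and pharmacokinetic profile disagree. That is a safeguard; it does not report laboratory error, and a mismatch does not in itself mean a wrong call.
- **That a number of children will carry a wrong genotype in their record.** This would need both an error rate and a referral rate, and the protocol gives neither.

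**Conclusion.** The inconsistency is real and does not depend on any numerical assumption. Within section 14.0, entry of the research genotype in the record is both barred and, on referral, required. Section 18.0 also removes the purpose that the provider bullet gives for the referral. The certain consequences are that staff have no single rule to follow and that some families would be told something that their own request makes untrue. Use by later prescribers is an inference from entry in the record. The label makes it less likely but does not exclude it.

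The reach is modest: an optional pathway, with no effect on in-study dosing, endpoints, analysis or sample size. It still merits correction, because it changes what staff do and costs little to put right. One limit remains. The Appendix L letters and the policy itself were not available for this review, so it cannot be said which of the two rules the institution intends.

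**What to change.** Reconcile the two bullets of section 14.0 and the text of section 18.0 to one rule, after checking the institutional policy that section 14.0 cites.

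- **Unless the policy permits labelled research entries:** amend the first two sentences of *Sharing Results with Providers*. Suggested wording: *If the family requests a referral to the GOLDILOKs Clinic, the referral note will ask for certified pharmacogenetic testing and will not contain the research genotype or phenotype. The result of the repeat test from a CAP/CLIA laboratory is the result to be documented.* This agrees with the participant bullet and with section 18.0.
- **If the policy does permit them:** correct the participant bullet and the family letter to say that a labelled research result will be entered when a referral is requested. Also reword the purpose of the referral so that it agrees with section 18.0.

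In either case, check that the Appendix L letters agree with the chosen rule, and review any entries already made under the provider bullet.

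The cost is a short amendment, a check of the letters and a search of the notes of referred participants. The study needs no new testing, because repeat certified testing is already the stated route and is already at the family's expense.

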## **15.0 Reimbursement, Payment and Tangible Property provided to subjects**

### **15.1 Payments**

Below is the payment schedule for activities related to participation in this study. Payments to subjects will be made via Greenphire. Families will be asked to provide a social security number for their child so that their child may be reimbursed.

Activity	Compensation
Completion of Research Visit 1	\$50.00
Completion of Research Visit 2, 0 –12 hours	\$200.00
Completion of Research Visit 2, 12 – 24 hours	\$60.00
Completion of Research Visit 2, return 48 hours	\$30.00
Completion of Research Visit 2, return 72 hours	\$30.00
Completion of Research Visit 3, 0 –12 hours	\$200.00
Completion of Research Visit 3, 12 – 24 hours	\$60.00
Completion of Research Visit 4, 0 –12 hours	\$200.00
Completion of Research Visit 4, 12 – 24 hours	\$60.00
Completion, return of drug taking calendar, and drug bottle at Research Visit 3	\$15.00
Completion, return of drug taking calendar, and drug bottle at Research Visit 4	\$15.00
Return of drug taking calendar and drug bottle at 6-Week Visit with Study Physician	\$10.00
Return of drug taking calendar and drug bottle at 12-Week Visit with Study Physician	\$10.00
Return of drug taking calendar and drug bottle at 18-Week Visit with Study Physician	\$10.00

Please note, visit length is expressed in hours post-drug administration.

The maximum compensation for participants in Study Design 1 is: \$950.00  
The maximum compensation for participants in Study Design 2 is: \$710.00  
The maximum compensation for participants in Study Design 3 is: \$830.00

## 16.0 Withdrawal of Subjects

### 16.1 Anticipated circumstances in which subjects will be withdrawn from the research study

- Participant experiences a serious adverse event and there is a probable association between the serious adverse event and study drug and/or research procedures.
- Participant experiences an adverse event, and there is a high probability of an association between the adverse event and study drug and/or research procedures and the adverse event interferes significantly with the participant's well-being (e.g. daily stomach aches).
- Participant requires care beyond what the research study team can provide while still meeting eligibility criteria (e.g. participant requires medication for tics that interferes with study drug).
- Participant is lost to follow-up.
- Participant is not compliant with study procedures.
- Participant revokes consent/assent.
- Participant no longer meets inclusion/exclusion criteria (e.g. abnormal safety labs).
- Participant does not have adequate response from ATX at 12-week visit and 18 week visit (<10% reduction in symptoms).

The PI may remove the participant from the study without the LAR's permission or participant's consent/assent if the above circumstances occur.

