18-Week Visit with Study Physician – The participant and family meet with a study physician approximately 6 weeks after the 12-Week Visit with Study Physician. A ± 2-week window is allowed for ease of scheduling. Prior to this visit, questionnaires will be sent out via CHADIS to parents and teachers to assess participant's behavior. During this visit, safety, efficacy, and side effects will be assessed and dose adjustments will be made accordingly. In addition, baseline questionnaires will be re-administered to gauge symptom and impairment changes post-treatment initiation. Dose adjustments may be outside research and visits with study physicians as needed.

Research Visit 4 – This visit is also referred to as pharmacokinetic study 3 (PK3) or end of study PK. This vist occurs after the 18-Week Visit with Study Physician. This visit takes place in the PCRU and consists of the same procedures as Research Visit 3. Determination of Study Design will be confirmed prior to visit, as some participants may require switching to a different study design if frequency of dosing has changed. During this visit, baseline psychometric measures will be re-administered to measure change post-treatment initiation. An end of study EKG will be obtained, and a Dietary Survey Questionnaire will be administered.

- Description of Research Procedures

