## **10. ADHD Care Following Conclusion of the Study**

Research personnel will call research participants and/or their parents two weeks ( $\pm$  1 week) following study conclusion or withdrawal from the study to check if any adverse events occurred in the interim. The research team will also take the opportunity to re-educate the family if a taper of medication was needed. This information will be documented on the 2-week Post-Study Completion Check CRF.

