### 16.2 Procedures for orderly termination/subject withdrawal

1. PI, Study Physician, or individual designated in the Delegation of Authority will contact the study participant and their family.
  - a. If the participant initiates the withdrawal, reasons will be documented and if applicable, intervention or plans for follow-up will made.
  - b. If the study team terminates the subject's participation in the study, study personnel will clearly explain the reasons for removal from the study and if applicable,

discuss next steps for necessary interventions or plan for follow-up care (e.g titration schedule for discontinuing study drug, etc).

2. If applicable, adverse events related to withdrawal will be promptly reported to the IRB per CM Policy 5.11 “Reportable Events”. Adverse events will continue to be followed until resolution.
3. Study personnel will complete end-of-study and withdrawal documentation in the subject binder.
4. All previously collected samples and data, regardless of whether participant completed the research study in its entirety, will be saved for data analysis.
5. Transfer of care procedures from the study physician to the participant’s primary care provider will take place in accordance with those outlined in section 11.6 for participants completing the study in its entirety.

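### A child withdrawn after starting atomoxetine but before Research Visit 4 has no scheduled on-treatment EKG, end-of-treatment labs, or post-baseline BRIEF, SCT or SCARED, because 16.2 provides no exit assessment

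*Combined protocol and SAP*

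**What the plan says.** Section 16.1 gives the circumstances for withdrawal. Some can arise at any time on drug: "Participant experiences a serious adverse event and there is a probable association between the serious adverse event and study drug and/or research procedures", a troublesome adverse event probably due to the drug, non-compliance, or a need for care that the study cannot give. One is tied to efficacy: "Participant does not have adequate response from ATX at 12-week visit and 18 week visit (<10% reduction in symptoms". The section heading is worded as if withdrawal follows. The closing sentence makes it discretionary: "The PI may remove the participant from the study without the LAR's permission".

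Section 16.2 has five items: contact and explanation, adverse event reporting with follow-up to resolution, paperwork ("Study personnel will complete end-of-study and withdrawal documentation in the subject binder"), retention of data already collected, and transfer of care. Transfer of care "will take place in accordance with those outlined in section 11.6 for participants completing the study in its entirety", but 11.6 is the biosafety section. The relevant text is in 11.5, which covers prescribing options such as "discontinuation or weaning of atomoxetine when deemed clinically appropriate" and schedules no test. Section 11.2 item 10 adds a phone contact that also covers withdrawals: "Research personnel will call research participants and/or their parents two weeks" (± 1 week) afterwards.

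On the timing of RV4, section 11.1 says: "This vist occurs after the 18-Week Visit with Study Physician".

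**The concern.** Children who leave early because of side effects or poor response are the ones in whom an end-of-treatment reading is most informative. The plan places those readings at a visit that these children may never reach, and 16.2 does not move them to the point of exit.

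Two things are at stake. The first is safety: section 11.3 relies on the RV4 EKG to look for cardiac injury after chronic dosing, and that check is skipped in early exits. The second is analytic: section 20.1 plans pre/post comparisons for BRIEF, SCT and SCARED. Their post-treatment values would be missing for reasons related to how the child did on the drug.

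**Working it through.** No power or sample-size figure is involved. The check is a count of scheduled assessments after the first dose.

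**Inputs**
- EKG: RV1 and RV4 only (Schedule of Events; 11.3; 11.4). RV1 precedes the drug.
- Safety labs: RV1 to RV4 (11.3). At RV2 they are signed off before the first dose (11.2), so only RV3 and RV4 are on treatment.
- BRIEF, SCT, SCARED: RV1 and RV4 only (Schedule of Events; 11.2).
- RV4 follows the 18-week visit (11.1).

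**Count of scheduled on-treatment assessments**

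| | Reaches RV4 | Leaves between RV3 and RV4 | Leaves before RV3 |
|---|---|---|---|
| EKG | 1 | 0 | 0 |
| Safety lab sets | 2 | 1 | 0 |
| BRIEF, SCT, SCARED (each) | 1 | 0 | 0 |

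**Does another provision fill the gap?** The five items of 16.2, section 11.5 and the 2-week call were read for any EKG, lab or scale. None names one.

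**Does RV3 stand in for RV4?** Only in part. RV3 gives labs, a physical exam, and heart rate and blood pressure at each draw, but no EKG and none of the three scales. It may fall after only two weeks of regular dosing. Section 5.1 starts at a target peak of 400 ng/mL and titrates to 600 or 800 ng/mL according to response, so RV3 can precede escalation.

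**The inadequate-response rule.** It needs both the 12-week and 18-week visits, so it can first be met at week 18, with RV4 the next research visit. Section 16.1 does not say which comes first. If removal precedes RV4, the middle column applies; if RV4 is done first, nothing is lost.

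**Direction of the analytic effect.** Let f be the fraction of treated children without RV4 scales, and D_c and D_w the mean improvement in children with and without them. A complete-case mean then exceeds the full mean by f × (D_c − D_w). This is favourable to the drug if D_w is smaller than D_c, which is plausible for poor responders but is an assumption. The documents give neither f nor the difference. The planning attrition of 20% (0.20 × 120 = 24, leaving 96) cannot stand in for f: it is all-cause, does not say how many leave after starting drug, and 8.2 counts partial completers, who need not reach RV4, toward the 120.

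**The case against.** The strongest reply is that the safety net is wider than the EKG. RV3 provides labs, an exam and serial vital signs. Physical exams are listed at weeks 6, 12 and 18 when the visit is in person. Adverse events are followed to resolution, 16.2 allows a follow-up plan, the 2-week call covers withdrawals, and the study physician may continue care and order tests. For an FDA-approved drug, clinically directed follow-up is defensible. All of this stands and keeps the point modest. It does not supply a scheduled EKG, closing labs or the three scales, and telehealth visits omit the exam.

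A reader might infer that every child meeting the inadequate-response rule loses the RV4 tests. The documents do not support that: removal is discretionary, 20.1 treats week 18 as the planned end of study, and no text says RV4 is skipped.

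A reader might also infer that tolerance is misclassified without an exit EKG. That does not follow. Section 4.2 ties intolerance to side effects that lead to stopping the drug, and 20.1 counts QT prolongation or dysrhythmia when it forces discontinuation. A child leaving for side effects is already intolerant. For a child leaving for poor response, an incidental EKG finding would not be the reason for stopping.

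Finally, none of the hypotheses in 2.2 uses change in BRIEF, SCT or SCARED, and 20.2 says weighting or imputation will be considered. Both are true. The pre/post analysis is still planned in 20.1, and retained symptom scores would help a missing-data method without replacing the absent scales.

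**Conclusion.** The gap is real and modest. Any child who starts atomoxetine and is withdrawn before RV4 has 0 scheduled on-treatment EKGs instead of 1, 1 or 0 on-treatment lab sets instead of 2, and 0 instead of 1 post-baseline reading on each of BRIEF, SCT and SCARED. For the inadequate-response group this holds only if removal takes effect before RV4, which 16.1 leaves open.

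The consequences are a skipped end-of-study cardiac check in early exits, alongside other monitoring that continues, and selective missingness in a secondary pre/post analysis. The main responder analysis is not shown to change: a child who reaches week 18 still has the Vanderbilt and the Clinical Global Impression scheduled there, and one who stops earlier for lack of efficacy despite dose escalation is classed as a non-responder by definition. The number of children affected and the size of any bias cannot be derived from the documents.

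The conclusion assumes that the withdrawal form and the DSMB documents, which were not available, add no exit assessment; nothing in the protocol text says that they do.

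**What to change.** In 16.2, add that any child who stops early after starting atomoxetine is offered the parent-report BRIEF and SCT and the SCARED, remotely if needed, plus the RV4 EKG and safety labs where feasible. These should be done before any taper if possible, and stopping the drug should not wait for them. The offer cannot reach a child lost to follow-up, or one who revokes consent or assent and declines.

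In 16.1, state that removal for inadequate response takes effect after RV4 unless continuing is unsafe or declined. Correct the transfer-of-care reference from 11.6 to 11.5; this is clerical.

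The cost is protocol and consent wording and one short optional visit with a needlestick, which some families will decline and which runs against the aim in 11.3 of fewer in-person procedures during the pandemic. The scales need little more than sending forms. Section 15.1 has no payment line for such a visit, so one may be needed. After an adverse event the drug may already be stopped, in which case the EKG and labs would not be on treatment. The RV4 post-dose PK/PD profile would remain missing.
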